11.1.2 Serious Adverse Events (SAEs)

An SAE is any untoward medical occurrence that:

- Results in death;
- Is life-threatening (i.e., event in which the subject was at risk of death at the time of the event; it does not refer to an event which hypothetically might have caused death if it were more severe);
- Requires inpatient hospitalization or prolongation of existing hospitalization (i.e., all medical events leading to hospitalizations will be recorded and reported as Serious Adverse Events, except for: hospitalization planned before inclusion into the study or out-patient treatment with no hospitalization). Note that an elective hospital admission will not be considered as a serious adverse event;
- Results in persistent or significant disability/incapacity (i.e., persistent or significant disability or incapacity” means that there is a substantial disruption of a person’s ability to carry out normal life functions);
- Is a congenital anomaly/birth defect

11.2 Event Reporting

We will capture all major potential adverse events related to antibiotic cessation/withholding in the combined primary safety outcome. The adverse outcomes

comprising the primary safety outcome will be included in outcome reporting and not reported a second time as Adverse Events (AE) or Serious Adverse Events (SAE).

However, as with any procedure or intervention, there may be adverse events that are currently unknown. Monitoring of AE is critical to the participants safety and data integrity. An AE will be defined as any untoward medical occurrence (unfavorable and unintended sign, symptoms or disease) in a participant temporally associated with the study intervention (eg. recommendation for cessation of antibiotics) but not necessarily related to participation in the study. A SAE will be defined as an untoward medical occurrence that results in death, is life-threatening or requires prolongation of ICU stay, results in disability or incapacitation.

AE and SAE will be recorded when reported by the treating team or study team nurse or when documented in the medical record. If a reportable SAE, the site PI will review the pertinent records (including medical notes, laboratory and radiographic data). The information, along with the site PI's impression of the diagnosis, will be recorded in the eCRF. The site PI will assess causality between the event and the intervention using best clinical judgement.

11.3 Criteria for Adverse Events related to antibiotics

Adverse event ¹	Definition
Non-C. difficile associated diarrhea	> 3 loose stools per day associated with Antibiotic use, in absence of laxative or pre-existing enteritis (C. diff excluded from this category)
C. Difficile infection	Clinical signs and symptoms consistent with CDI and PCR test positive (and no laxatives)
Nausea/vomiting	Nausea and vomiting associated with antibiotic administration, in the absence of alternative explanation
Hematologic	Anemia: hemoglobin <10g/dL Leucopenia: WBC < 4500 cells/uL Thrombocytopenia: platelets <150x10 ³ /uL with levels below patient's baseline and in absence of bleeding or myelosuppressive therapy
Hepatobiliary	Cholestasis (bili > 51umol/L) or transaminitis (ALT, AST > 3x baseline) in the absence of existing hepatobiliary disease or recent biliary instrumentation
Renal	Increase in serum creatinine > 1.5x patient's baseline in the absence of precipitating factors such as intravenous contrast or other nephrotoxic agents, and not related to sepsis
Neurologic	Altered mental status, peripheral neuropathy, seizures in the absence of pre-existing neurological conditions or substance-related toxic events and unrelated to infectious syndrome
Dermatologic	Rash, including hives, non-hives rashes, red man syndrome – temporally associated with antibiotics; resolution with antibiotic cessation

Cardiac	QTc>440 ms in males or >460ms in females in absence of pre-existing arrhythmias, based on >2 ECGs
Anaphylaxis	Acute onset respiratory compromise, hypotension, or end organ dysfunction within minutes after antibiotic administration, without alternative explanations
Myositis	Increase in creatine kinase level >5 x patient's baseline, in absence of statin use or pre-existing myopathy

¹Adapted from Tamma et al, JAMA 2017

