12.2 Definitions for clinical outcomes and ranking of outcome categories (DOOR)

Points are assigned for overall outcomes, with pre-specified definitions for treatment failure, complications and adverse events related to antibiotic use. All clinical outcomes will be reviewed by a 3-member clinical review panel, and all AE will be reviewed by a different 3-member panel (the Data Safety and Monitoring Committee). The panels will consist of experienced ID, Pharmacy and ICU experts (to be named) blinded to intervention and patient identity.

Clinical outcome	Definition
Treatment failure	Signs and symptoms of initial event (infectious illness) within 72h of end of antibiotic treatment
Infection persistence	Continued presence of signs and symptoms and of original causative pathogen at end of antibiotic treatment
Infection recurrence	New infection due to at least one of the original causative agents found at baseline (initial event)
Infectious complication	Signs and symptoms requiring surgical or other procedure in organ involved in initial event (eg. empyema post pneumonia) occurring >72h after end of antibiotic treatment

We will determine how many DOOR events (AE, infection recurrence etc.) occurred for each participant, then assign a mutually exclusive rank.

RANK	Criteria
1	Survival, clinical benefit of treatment, with NONE of treatment failure, persistence, recurrence, complication AND NONE of Grade IV adverse event (AE)
2	Survival, clinical benefit of treatment, with NONE of treatment failure, persistence, recurrence, complication, AND at least one of AE
3	Survival, at least one of treatment failure, persistence, recurrence, complication, AND NONE of AE
4	Survival, at least one of treatment failure, persistence, recurrence, complication AND at least one AE
5	Death

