12.4 Sample Size and Justification

DOOR-RADAR requires fewer patients than conventional non-inferiority analysis but since a major objective of this study is to enable a detailed analysis of adverse events related to antibiotic use, we have calculated a sample size that would enable separate analysis of clinical outcomes and antibiotic use (Sample size calculations detailed in Appendix I).

Testing hypothesis 1 (H1): We desire at least 80% power to test our primary hypothesis that BV-supported antibiotic treatment decision can lead to reducing antibiotic exposure using a one-sided significance of 0.05. Demonstrating H1 would require a sample size of 352 participants per group for a mean difference in antibiotic days of 1.5 (SD 8 days). Based on studies evaluating AMS interventions in the ICU, we estimate a 1.5 days difference between the 2 groups to be significant^{14,18,36}. Further, it would be equivalent to a 20% decrease in total antibiotic days, a reasonable assumption considering antibiotics are “clearly not indicated” or “only somewhat (dubious) indicated” in about 30% of cases based on prior retrospective audits of prescription quality.

Testing hypothesis 2 (H2): BV-supported antibiotic treatment algorithm does not lead to worse clinical outcomes. Studies using combined endpoints of adverse outcomes have estimated between 10-25% rates of combined adverse outcomes (death, septic shock, mechanical ventilation, renal failure)^{38,42,43}. A meta-analysis of PCT-guided antibiotic treatment in patients with infection and sepsis in ICU reported all-cause mortality rates of 23% at 30-days³⁵. Studies evaluating adverse events specifically related to antibiotic use in hospitalized patients suggest rates of 12% within 30 days. We expect a combined adverse outcome rate of 18-20% and will set a non-inferiority margin at 4%. A sample size of 529 patients per group (1060 in total) will therefore provide 80% power to demonstrate H2 (a robust safety evaluation), and yet be exceptionally well powered for efficacy (with preserved power under a wide range of assumptions).

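### The hematologic adverse-event criterion in section 11.3 asks for no minimum fall and no repeat value, so a stable patient already under a cut-off will probably meet it through laboratory variation alone

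*Protocol*

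**What the plan says.** The hematologic row of the table in Protocol section 11.3 has three items. The first two are "Anemia: hemoglobin <10g/dL Leucopenia: WBC < 4500 cells/uL" and the third is platelets under 150 x 10³/µL. The row ends with the condition "levels below patient's baseline and in absence of bleeding or myelosuppressive therapy". No minimum fall, repeat value or definition of baseline is given there or elsewhere. As printed, the condition follows the platelet item, so it is not certain that it also governs hemoglobin and white cells.

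Other rows are stricter. The table asks for "Increase in serum creatinine > 1.5x" baseline in the renal row, "transaminitis (ALT, AST > 3x baseline" in the hepatobiliary row and "Increase in creatine kinase level >5 x" baseline for myositis. The QTc item must rest on more than two ECGs.

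Sections 8.4 to 8.7 collect hematology values at Day 0 and at Days 1, 3, 7, 14 and 28. Sections 9.2 and 9.3 limit these to results that the treating team ordered. The entry criteria in 4.2 and 4.3 do not exclude ordinary anemia, leucopenia or thrombocytopenia; the only blood-count exclusion is profound neutropenia with chemotherapy.

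Section 12.4 says that "a major objective of this study is to enable a detailed analysis of adverse events related to antibiotic use" and uses this to justify a sample larger than DOOR-RADAR needs.

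**The concern.** For a patient already under a cut-off at Day 0, the cut-off does no work, and the event threshold becomes the baseline reading itself. A hemoglobin of 9.6 g/dL on Day 0 and 9.5 on Day 3, without bleeding, satisfies the row. If the baseline condition belongs to platelets only, an unchanged 9.6 satisfies it too.

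Such events arise in both arms without any drug effect. In a comparison of antibiotic adverse events they dilute true toxicity. A false-event share f that is equal in both arms multiplies the true risk difference by (1 − f) and, at event rates below one half, also raises the variance. Real benefit and real harm both become harder to see.

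**Working it through.** **1. Stable patient who stays under a cut-off.** Assume a constant true level and exchangeable errors. One baseline and k follow-up values are then equally likely to come in any order. The criterion is missed only if the baseline is the lowest of the k + 1 values, so, ignoring ties,

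P(at least one follow-up value below baseline) = 1 − 1/(k + 1) = k/(k + 1).

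This gives 50% for k = 1, 67% for k = 2, 75% for k = 3, 80% for k = 4 and 83% for k = 5. The shape of the error distribution does not matter.

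**2. Patients near or above a cut-off.** This was simulated with 200,000 stable patients, one baseline and five follow-up values, normal variation and usual reporting precision. The within-patient coefficients of variation (CV) are assumptions, not figures from the Protocol: hemoglobin 3–8%, white cells 10–20%, platelets 5–12%.

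| True level | Meets the criterion at least once in 5 values |
|---|---|
| Hemoglobin 9.0 g/dL | 79–82% |
| Hemoglobin 10.5 | 18–69% |
| Hemoglobin 11 | 0.4–43% |
| Hemoglobin 12 | 0–8% |
| White cells 4.0 x 10³/µL | 80–82% |
| White cells 5.0 | 48–72% |
| White cells 9.0 | 0–3% |
| Platelets 140 x 10³/µL | 82–83% |
| Platelets 160 | 37–73% |
| Platelets 220 | 0–2% |

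Rounding creates ties, so the figures under a cut-off lie slightly below 83%. The effect fades quickly above the cut-offs.

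**3. Scale against the Protocol's own rate.** Section 12.4 cites 12% within 30 days for antibiotic adverse events. If a share s of participants sits stably under one cut-off, the false share is s × k/(k + 1). It equals 12% when s = 0.12/0.50 = 24% with one follow-up value, or s = 0.12/0.80 = 15% with four. The Protocol does not give s.

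**4. Which safeguard works.** The simulation was repeated with a repeat value alone, and with an illustrative fall of at least 20% from baseline.

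| Stable patient, 5 values | As written | Two consecutive values below baseline | Fall ≥20%, any value | Fall ≥20%, confirmed |
|---|---|---|---|---|
| Hemoglobin 9.0, CV 5% | 81% | 51% | 0.5% | under 0.1% |
| Platelets 140, CV 8% | 82% | 53% | 10% | about 1% |
| White cells 4.0, CV 15% | 81% | 51% | 44% | 12.5% |

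A repeat value alone leaves about half, because one high baseline reading makes every later value look like a fall. The size of the fall does most of the work, and white cells need a larger one than hemoglobin.

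A rule that accepts either a new crossing of the cut-off or a fall of 2 g/dL does less well. Take an assumed hemoglobin distribution: mean 9.5–11.5 g/dL, between-patient SD 1.5, within-patient SD 0.3–0.6, one to four follow-ups. On a single value, that rule leaves about 3–18% false events across all participants, or about 1–7% with two consecutive values. Making the 2 g/dL fall mandatory leaves at most about 3%.

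**The case against.** The strongest reply is that the table is not a machine rule. Under 11.2 and 11.3.1 an event is recorded when the treating team or study nurse reports it or when it is charted. Under 12.2 a blinded three-member panel reviews every adverse event. A drift of 0.1 g/dL may never be charted. This stands in part: the percentages above describe qualifying laboratory values, not recorded events. It does not remove the problem. Hematology values are collected at each visit, and the panel works to these same pre-specified definitions. CTCAE grading (11.3.2) grades an event; it does not decide whether one occurred.

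A second reply is that follow-up values may be few. Blood counts are routine-care only, and 12.6 gives a median stay of 3.2 days. That lowers k, but one value already gives 50%.

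A third is that the table is adapted from a published study. That does not alter what the row does in ICU patients who are measured repeatedly.

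Three stronger readings are tempting, and the documents do not support them:

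- **That stable survivors are pushed down the DOOR ranks.** Rank 2 reads "Survival, clinical benefit of treatment, with NONE of treatment failure, persistence, recurrence, complication, AND at least one of AE" with no grade. However, Rank 1 introduces the abbreviation as a Grade IV event, and 12.2 requires mutually exclusive ranks. If any grade counted in Rank 2, a survivor with only a low-grade event would fit both ranks. The Grade IV reading is the likelier one, and under it small laboratory falls would rarely change a rank.
- **That a given percentage of all participants will be misclassified.** With the hemoglobin distributions assumed in step 4 and the rule as written, the result runs from about 8% to 60%. That spread reflects the assumptions, not the Protocol.
- **That H2 loses power.** The stated 529 per group reproduces: (1.645 + 0.842)² × (0.20 × 0.80 + 0.18 × 0.82)/(0.04 + 0.02)² gives 529. If 10% false events entered both arms, the rates would be 28% and 26.2%, and power at 529 would fall from 80% to 68%. Section 12.4 does not say that any-grade hematologic events enter that composite, so this stays conditional.

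**Conclusion.** The point holds for the definition and for the any-grade antibiotic adverse-event analysis. As written, the row cannot separate a drug effect from laboratory variation in patients who start under a cut-off. Such a stable patient meets it with probability about k/(k + 1). Patients close above a cut-off are affected to a degree that depends on the assumed variation; those well above are hardly affected.

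The k/(k + 1) result rests on a constant true level, exchangeable errors and few ties. The Grade IV incidence objective in 3.2.2 is little exposed, and so is DOOR if its events are Grade IV. Charting and panel review reduce the number of false events by an amount the documents do not allow one to estimate. The row should be corrected, but it does not by itself put the primary comparison in doubt.

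**What to change.** Amend the hematologic row in 11.3 as follows:

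- Define baseline as the Day 0 value.
- State that the baseline condition applies to hemoglobin, white cells and platelets alike.
- Require for each item a pre-specified minimum fall from baseline in addition to the cut-off. The investigators should set its size item by item, in line with the other rows and allowing for the greater variability of white cells.
- Require confirmation on the next routine value where one is available.
- State that a new crossing of the cut-off without the minimum fall does not suffice.

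The cost is one table row and a derivation in the eCRF. No new blood tests are needed, and participants already enrolled can be classified from values already collected. The change is best made before the first interim analysis. The downside is that a few mild true events will no longer be counted.

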4.1 Number of Participants

Our target recruitment goal is 600 participants per group (1200 total participants) at participating MUHC sites.

During the pilot phase of the study, it was documented that the study population in ICU are often incapable of providing informed consent for themselves due to their health condition or due to the fact they are intubated. As of 17-Jun-2025, 40% of otherwise eligible patients could not be approached by the research team as they suddenly lost their capacity to consent for themselves. Without the possibility to approach the Legally Authorized Representative who makes health decisions on behalf of the patient, there is a significant risk the BAST-ICU trial may not meet its enrollment target therefore study objectives.

As this study represents minimal risks to participants, that medical decision-making remains in the treating team's hands, and the objectives of the study would not be met if only patients with capacity to consent are approached, the inclusion criteria are updated to include:

- Participant who have suddenly lost capacity to consent due to their health condition (intensive care) and for whom a Legally Authorized Representative can be approached and provide consent for the patient. The research team will seek the participant's consent (confirmation of consent or withdrawal) as soon as the participant regains capacity to consent.

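### The cardiac adverse-event criterion in 11.3 has no comparison with the patient's own baseline and no exclusion for a competing drug; the neurologic row has a narrower gap on onset and sedation

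*Protocol*

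**What the plan says.** The table in protocol section 11.3 sets the criteria for adverse events related to antibiotics. The cardiac criterion reads "QTc>440 ms in males or >460ms in females in absence of pre-existing arrhythmias, based on >2 ECGs". The neurologic criterion reads "Altered mental status, peripheral neuropathy, seizures in the absence of pre-existing neurological conditions or substance-related toxic events" and adds that the event must be "unrelated to infectious syndrome".

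Other rows of the table are built differently. The renal row reads "Increase in serum creatinine > 1.5x patient's baseline in the absence of precipitating factors such as intravenous contrast or other nephrotoxic agents", the myositis row "Increase in creatine kinase level >5 x patient's baseline, in absence of statin use or pre-existing myopathy", and the hematologic row carries the condition "with levels below patient's baseline and in absence of bleeding or myelosuppressive therapy".

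Three other places bear on how much this matters:
- Section 11.3.2 grades all adverse events by CTCAE.
- Section 12.2 sends all adverse events to a blinded three-member panel and defines DOOR rank 1 with "AND NONE of Grade IV adverse event (AE"). Ranks 2 to 4 mention adverse events without a grade.
- Section 12.4 names detailed analysis of antibiotic-related adverse events as a major objective and a reason for the chosen sample size.

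**The concern.** An adverse event attributed to a drug should be new or worse since the drug was started and not better explained by something else. The renal and creatine kinase rows ask for both. The cardiac row asks for neither. Many ICU patients could have a QTc above the threshold before the antibiotic, or because of another drug, and the row as written does not separate these from antibiotic effects.

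The neurologic row is better protected, but it has no onset condition. In a population that is often sedated or ventilated, it is not clear whether a patient under therapeutic sedation, or with delirium of non-infectious cause, meets it.

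The stake is the quality of the adverse event comparison. Events unrelated to the antibiotic occur at about the same rate in both arms, so they raise both rates and shrink a true difference. For a superiority comparison that costs power. For a non-inferiority comparison it makes a real harm look smaller.

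**Working it through.** **Step 1. The rows of the 11.3 table side by side.**

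| Row | Compared with patient's baseline | Tied to the antibiotic | Competing causes excluded |
|---|---|---|---|
| Renal | yes (1.5 times) | no | contrast, other nephrotoxic agents, sepsis |
| Myositis (CK) | yes (5 times) | no | statins, prior myopathy |
| Hematologic | yes | no | bleeding, myelosuppressive therapy |
| Hepatobiliary | transaminases yes, bilirubin no | no | existing disease, instrumentation |
| Diarrhea, nausea/vomiting, rash, anaphylaxis | no | yes | varies |
| Neurologic | no | no | prior neurological condition, toxic event, infection |
| Cardiac | no | no | prior arrhythmia only |

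Take a man with a QTc of 450 ms before the antibiotic and 450 ms on repeat ECGs afterwards. He exceeds 440 ms, and a long QTc is not in itself an arrhythmia, so he meets the cardiac criterion with no change at all. Requiring several ECGs guards against measurement error, not against a long-standing value.

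**Step 2. The plan's own H2 figure.** Inputs from 12.4 and Appendix I: 20% control, 18% BV, margin m = 0.04, one-sided 0.05, power 80%.

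n = [pC(1−pC) + pT(1−pT)] × (1.645 + 0.842)² / (m − (pT − pC))²
= (0.16 + 0.1476) × 6.183 / 0.06² = 528.3, so 529 per group. The plan's figure reproduces; the sample size table is not in question.

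**Step 3. Illustration of dilution.** Assume that a share b of patients in each arm meets a criterion for a reason unrelated to the antibiotic, independently of genuine events, and that such events enter the H2 composite. The protocol gives no b; 5 to 20% is an assumption. Then:

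- observed rate = p + b(1 − p), so a true difference d is observed as (1 − b)d;
- probability of declaring non-inferiority = Φ((m − observed difference)/SE − 1.645), with SE = √{[pC(1−pC) + pT(1−pT)]/600}, using the 600 per group of section 4.1.

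Example with b = 10% and a true harm of 24% v 20%: pC = 0.20 + 0.10 × 0.80 = 0.28; pT = 0.24 + 0.10 × 0.76 = 0.316; SE = √[(0.2016 + 0.2161)/600] = 0.0264; Φ(0.004/0.0264 − 1.645) = Φ(−1.49) = 6.8%.

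| b | Planned case, control / BV | n per group for 80% | Power at 600 | True 4-point harm observed as | Chance it passes |
|---|---|---|---|---|---|
| 0 | 20.0% / 18.0% | 529 | 84% | 4.0 | 5.0% |
| 5% | 24.0% / 22.1% | 630 | 78% | 3.8 | 5.9% |
| 10% | 28.0% / 26.2% | 726 | 73% | 3.6 | 6.8% |
| 20% | 36.0% / 34.4% | 900 | 65% | 3.2 | 8.7% |

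**The case against.** The strongest reply is that the protocol has other safeguards.

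- **Grade.** Rank 1 is defined by the absence of Grade IV events, and the abbreviation for adverse event is introduced in that phrase. The synopsis and section 3.2.2 also speak of Grade IV. On that reading a QTc 10 ms over the threshold would probably not change a DOOR rank. This largely stands for DOOR. Because ranks 2 to 4 carry no grade, the text does not settle it, and it does not cover the separate analysis of antibiotic-related events.
- **Panel and title.** The section is headed as events related to antibiotics, section 11.2 asks for temporal association with the intervention, and blinded experts review each event. Experts may well discard an unchanged QTc. But section 12.2 has them work from pre-specified definitions, and blinding does not supply a missing clause. Association with a study recommendation is also not the same as onset after the antibiotic.
- **Neurologic exclusions.** The row has three, and the one for toxic events could be read to include sedatives. This stands, and it is why the neurologic point is only one of clarity.
- **Uniformity.** Bilirubin and C. difficile also lack a baseline clause, so the table is not uniform apart from these two rows. True, but this does not repair the cardiac row.

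A reader might go further and take the 40% in section 4.1 as a false-event rate. The documents do not support that: the sentence is "40% of otherwise eligible patients could not be approached by the research team as they suddenly lost their capacity to consent for themselves". It measures lost capacity, and it may include patients whose state is due to infection or neurological disease, whom the neurologic row excludes.

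**Conclusion.** The cardiac criterion is deficient as written: it can count a QTc that predates the antibiotic or is due to another drug. The neurologic criterion needs clarification on onset, sedation and non-infectious delirium.

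The likely effect is non-differential noise, because patients are randomized and review is blinded. The text gives no reason to expect that one arm is favoured. Nor does it support the inference that pre-existing states will generally be scored as antibiotic events, or that DOOR ranks will shift widely; if only Grade IV events count, the effect on rank is small.

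The size cannot be computed from the documents. The rise from 5% to between 5.9% and 8.7% in the chance of passing a true 4-point harm rests on an assumed 5 to 20% false scoring, equal in both arms and independent of genuine events, and on these events entering the H2 composite. The case for change rests on the wording and on the stated importance of the adverse event analysis, not on that range.

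**What to change.** In the table of section 11.3:

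- **Cardiac row:** require an increase over the patient's last available ECG before the antibiotic, and the absence of another newly started QT-prolonging drug. The renal and creatine kinase rows are the model.
- **Neurologic row:** require onset or worsening relative to the charted state before the current antibiotic course, and state that effects of sedation and delirium of other cause are excluded. Day 0 should not be the reference: under section 4.2 antibiotics may have started up to 72 hours earlier, so a Day 0 baseline could discard true antibiotic neurotoxicity.
- **Adverse event form:** add the pre-antibiotic QTc and mental status with dates, and the competing drugs or causes considered.

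These are changes to endpoint definitions, not to patient care. The cost is two table rows plus the form fields. Neither ECG nor mental status is named in the data lists of sections 8.3 to 8.7, 8.11 and 9.2, so some extra chart abstraction is needed, but no new test. The downside is that a few true events without a documented pre-antibiotic value go uncounted; reporting them separately as indeterminate keeps them visible.
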